Brief Cognitive-Behavioral Therapy for Suicide Prevention in a Brazilian Outpatient Sample (BCBT-BR): Protocol for a Two-Arm Randomized Controlled Trial

Short title: BCBT-BR Trial Protocol

Date: May 4th, 2026

Abstract

Importance: Suicide remains a leading cause of premature mortality worldwide. While global rates have declined since 2000, the Region of the Americas shows concerning increases, particularly in Brazil. Brief Cognitive-Behavioral Therapy (BCBT) has demonstrated efficacy in reducing suicide attempts in high-income countries, but evidence from low- and middle-income countries (LMICs) and civilian outpatient settings remains limited.

Objective: To evaluate whether BCBT reduces suicide attempt incidence over 6 months compared with manualized Supportive Psychotherapy (ST) among high-risk Brazilian adults receiving university outpatient care.

Design, Setting, and Participants: Single-site, parallel-group, superiority randomized clinical trial (RCT) at the Institute of Psychiatry, University of São Paulo, Brazil. Adults aged 18-65 years with current suicidal ideation and/or suicide attempt within the past month will be randomized 1:1 to receive 12 weekly 60-minute sessions of BCBT or dose-matched ST (N=150; 75/group).

Interventions: BCBT targeting emotion regulation and cognitive reappraisal versus manualized ST providing emotional support without systematic skills training.

Main Outcomes and Measures: Primary outcome is time-to-first suicide attempt over 6 months, assessed by blinded evaluators. Secondary outcomes include suicidal ideation, non-suicidal self-injury, depression, anxiety, treatment feasibility and acceptability. Assessments occur at baseline, mid-treatment (week 6), end-of-treatment (week 12), and 3- and 6-month follow-ups, with weekly attempt surveillance. Intention-to-treat analyses will employ Cox proportional hazards regression (primary outcome) and mixed-effects/generalized linear models (secondary outcomes). Sample size provides 80% power to detect HR=0.50 ($\alpha=0.05$, 25% attrition).

Conclusions and Relevance: This trial will provide critical evidence on BCBT effectiveness in LMIC outpatient settings, informing scalable suicide prevention strategies.

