Secondary objectives: Compare trajectories of suicidal ideation, NSSI, depression, and anxiety; evaluate feasibility/acceptability; explore predictors and moderators of response (e.g., prior attempts, sex, age, symptom severity).

Hypotheses

1. BCBT will yield a lower hazard of suicide attempt (superiority).

2. BCBT and ST will show similar improvements in general anxiety/depression, but BCBT will outperform ST on suicide-related outcomes.
3. BCBT will demonstrate high feasibility and acceptability in this population, as reflected by satisfactory recruitment rates, session attendance, treatment adherence, and positive patient satisfaction ratings.
4. Baseline characteristics, including history of prior suicide attempts, baseline symptom severity, age, and sex, will be associated with differential clinical outcomes over follow-up.

Methods

Trial Design

Single-site, parallel-group, superiority RCT (1:1) with blinded outcome assessment and 6-month follow-up. The protocol follows the SPIRIT 2025 guidelines; reporting will follow the CONSORT 2025 guidelines and the extensions for non-pharmacological interventions and harms.

Randomization

Participants will be randomly assigned in a 1:1 ratio, stratified by sex and prior suicide attempt, using a computer-generated permuted-block randomization sequence with variable block sizes (blocks of 4 and 6) to prevent allocation prediction. The sequence will be generated by an independent researcher with no involvement in participant recruitment or outcome assessment, using validated statistical software. Participants will be enrolled by the study coordinator; treatment allocation will be released only after eligibility is formally confirmed and informed consent is obtained. Allocation concealment will be maintained through a centralized, web-based randomization module within REDCap, which withholds the assigned arm until the enrollment step is completed and locked. Neither the enrolling clinician nor the participant will have access to forthcoming allocations.

Blinding

Given the nature of psychotherapy research, blinding of participants and therapists to treatment allocation is not feasible (Cuijpers et al., 2015). However, all outcome

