These outcomes will be assessed using the Beck Scale for Suicide Ideation (BSI) for suicidal ideation; the Columbia–Suicide Severity Rating Scale (C-SSRS) for suicidal ideation and behavior; the SAFER and SAFER Follow-Up scales for high-risk self-harm monitoring; the Beck Depression Inventory–II (BDI-II) and Montgomery–Åsberg Depression Rating Scale (MADRS) for depressive symptoms; the Generalized Anxiety Disorder-7 (GAD-7) for anxiety; the Patient Health Questionnaire-9 (PHQ-9) for depression severity; the Deliberate Self-Harm Inventory–short form (DSHI-s) for nonsuicidal self-injury; the Duke University Religion Index (DUREL) for religiosity; the Purpose in Life Test (PIL) for perceived meaning in life; the Subjective Happiness Scale (SHS) for subjective well-being; the Short-Form Health Survey-12 (SF-12) for health-related quality of life; the Hypomania Checklist-32 (HCL-32) for hypomanic symptoms; the PROMIS Sleep Disturbance instruments for sleep-related functioning; the NIH Brief Fatigue Inventory for fatigue (NIH - BFI); Fatigue Severity Scale (FSS) and the Suicide Cognitions Scale–Revised (SCS-R) for suicide-specific maladaptive cognitions. A sociodemographic and clinical scale developed by the authors will assess participants' demographic characteristics, psychiatric history, prior suicide attempts, treatment history, and current clinical status. See Table 2 in Supplementary Material for assessment schedule.

Beck Scale for Suicide Ideation (BSI)

The Beck Scale for Suicide Ideation (BSI), developed by Beck & Steer (1991), is a self-report scale designed to identify the presence of suicidal ideation and assess associated factors, including suicide plans, behaviors, and attitudes. The scale consists of 21 items, each with three possible responses, and is used to measure the intensity of suicidal thoughts (Beck & Steer, 1991). The BSI was translated and validated for the Brazilian population by Cunha (2001), with its psychometric properties found to be satisfactory in both clinical and non-clinical samples.

Beck Depression Inventory–II (BDI-II)

The BDI-II is a 21-item self-report inventory assessing depressive symptom severity over the previous two weeks. Items cover cognitive, affective, and somatic features

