- Primary analysis: Cox model estimating HR for BCBT vs ST, adjusting for stratification factors (sex, prior suicide attempt), with additional covariates (age and baseline suicidal ideation) included in sensitivity analyses. Check proportional hazards (Schoenfeld residuals); if violated, use time-varying effects or restricted mean survival time. Given approximately 17 anticipated events, including four covariates yields an events-per-variable (EPV) ratio of ~4, below the commonly recommended threshold of 10. To reduce the risk of overfitting, the pre-specified primary model will include only the two stratification factors (sex and prior suicide attempt) as covariates (EPV ~8.5). Adjustment for age and baseline suicidal ideation will be conducted as a supplementary sensitivity analysis.
- Secondary analyses: Linear mixed-effects models (random intercepts) for fixed effects: time, group, group×time; GEE/logistic models for binary outcomes (e.g., any NSSI).
- Missing data: Missing At Random (MAR) is defined as missingness that depends only on observed data; Missing Not At Random (MNAR) refers to missingness that depends on unobserved data (e.g., patients drop out because their suicidal ideation worsened). Time-to-event outcome: participants lost to follow-up will be censored at the date of last confirmed contact. Sensitivity analyses will include: (a) best-case scenario—all BCBT dropouts are assumed attempt-free (censored at day 180) while all ST dropouts are assumed to have attempted at their last contact date; (b)

worst-case scenario—the reverse; (c) tipping-point analysis—identifying the minimum assumed increase in hazard for censored BCBT participants that renders the primary result non-significant.

- Exploratory moderators (hypothesis-generating only): These analyses are explicitly exploratory. Given the projected sample size and anticipated number of primary events, treatment-by-baseline interaction tests are underpowered for definitive subgroup inference and must not be interpreted as confirmatory evidence of effect heterogeneity. Interactions of treatment with baseline factors (e.g., prior attempt, sex, age, baseline symptom severity) will be examined with marginal effects and graphical probes. Mediation (e.g., change in cognitive distortions) may be explored descriptively if data allow. All findings will be framed as generating hypotheses for future adequately powered trials.

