- Multiplicity: The primary outcome (time-to-first suicide attempt) is the sole pre-specified confirmatory endpoint, tested at two-sided $\alpha=0.05$. Secondary outcomes are organized in the following interpretive hierarchy: (1) suicidal ideation (BSI, C-SSRS ideation subscale); (2) non-suicidal self-injury (DSHI-s); (3) depressive symptoms (BDI-II); (4) anxiety (GAD-7); (5) treatment feasibility and acceptability. No formal α -adjustment is planned across secondary outcomes; results should be interpreted in light of the number of comparisons made and regarded as exploratory. Exploratory moderator and mediator analyses carry no inferential weight regarding treatment efficacy and will be clearly labelled as hypothesis-generating throughout the manuscript.

Data capture and management

REDCap with role-based access, audit trails, range checks, and encrypted storage. Identifiers stored separately; audio files on secure institutional servers. Only authorized personnel access identifiable data.

Monitoring and safety

Independent Data and Safety Monitoring Board (DSMB) reviews SAEs quarterly (or ad hoc) and may recommend protocol modifications or early termination for safety. AEs/SAEs reported to CEP/CONEP per Brazilian regulation. Participants receive 24/7 emergency contacts.

Discussion

The BCBT-BR trial rigorously evaluates whether suicide-specific CBT confers advantages over common-factor ST in a Brazilian outpatient setting. Strengths include an active comparator, blinded assessment, event-focused primary outcome, therapist cross-training with fidelity checks, and cultural adaptation. Findings will guide scalable implementation of suicide-focused care in LMIC public mental health systems.

Ethics and Registration

Ethics: CONEP/Plataforma Brasil approval CAAE 88755725.9.0000.0068

Registration: ClinicalTrials.gov [registration pending; CAAE 88755725.9.0000.0068 refers to the Brazilian ethics approval (CONEP/Plataforma Brasil) and is reported separately above] 88755725.9.0000.0068

Protocol amendments: Any substantial changes will be submitted to ethics committees and updated in registries.

Funding

There is no funding for this trial. RFD receives scholarship from São Paulo Research Foundation (FAPESP) (#2024/10058-0).

Author Contributions

- Conceptualization: [name] (LB), [name] (RFD), [name] (ECM), [name] (CB)
- Methodology: LB, [name] (RERF), CB, RFD

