
Supplementary Material

Table 1: The structure and components of BCBT (Bryan & Rudd, 2018)

Phase	1	2	3
Sessions	1-5	6-10	11-12
Therapeutic component	Emotional Regulation and Crisis Management	Targeting Belief Systems Related to Suicide	Relapse Prevention
Techniques	Crisis Response Plan; Means restriction counseling; Sleep stimulus control; Relaxation skills training; Mindfulness skills training; Reasons for living list; Survival kitk.	ABC Worksheet ; Challenging Questions Worksheet; Problematic Patterns of Thinking Worksheet; Activity planning; Coping cards.	Relapse prevention task.

Table 2: Assessment schedule

Schedule of Assessments (CONSORT format)

Measure	T0	T1	T2	T3	T4	T5	T6	T7	T8	T9	T10	T11	T12	T13	T14	T15
Sociodemographic	X															
Treatment History	X															
Weekly Follow-up		X	X	X	X	X	X	X	X	X	X	X	X	X	X	X
BSI	X	X	X	X	X	X	X	X	X	X	X	X	X	X	X	X
BDI-II	X	X	X	X	X	X	X	X	X	X	X	X	X	X	X	X
DUREL	X	X	X	X	X	X	X	X	X	X	X	X	X	X	X	X
GAD-7	X	X	X	X	X	X	X	X	X	X	X	X	X	X	X	X
PHQ-9	X	X	X	X	X	X	X	X	X	X	X	X	X	X	X	X
PIL	X	X	X	X	X	X	X	X	X	X	X	X	X	X	X	X
SHS	X	X	X	X	X	X	X	X	X	X	X	X	X	X	X	X
SF-12	X	X	X	X	X	X	X	X	X	X	X	X	X	X	X	X
HCL-32	X	X	X	X	X	X	X	X	X	X	X	X	X	X	X	X
PROMIS Sleep	X	X	X	X	X	X	X	X	X	X	X	X	X	X	X	X
MADRS		X	X	X	X	X	X	X	X	X	X	X	X	X	X	X
C-SSRS		X	X	X	X	X	X	X	X	X	X	X	X	X	X	X
NIH BFI		X	X	X	X	X	X	X	X	X	X	X	X	X	X	X
FSS		X	X	X	X	X	X	X	X	X	X	X	X	X	X	X
SCS-R	X	X	X	X	X	X	X	X	X	X	X	X	X	X	X	X
SAFER	X	X	X	X	X	X	X	X	X	X	X	X	X	X	X	X
SAFER Follow-Up														X	X	X

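### Table 2 never schedules the DSHI-s, the instrument for the second-ranked secondary outcome, and leaves C-SSRS, MADRS, NIH BFI and FSS without a baseline mark

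*Protocol*

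**What the plan says.** **Ranking and model.** The Multiplicity paragraph of the protocol's Statistical analysis plan sets an interpretive order for the secondary outcomes. First comes "1) suicidal ideation (BSI, C-SSRS ideation subscale", and second "2) non-suicidal self-injury (DSHI-s". Depression is ranked third by BDI-II and anxiety fourth by GAD-7. Under Secondary analyses, continuous outcomes get "Linear mixed-effects models (random intercepts) for fixed effects: time, group, group×time". Binary outcomes get GEE or logistic models, with any NSSI as the example. Comparing NSSI trajectories is also a stated secondary objective.

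**Instrument.** The Instruments section names "the Deliberate Self-Harm Inventory–short form (DSHI-s) for nonsuicidal self-injury" and closes with "See Table 2 in Supplementary Material for assessment schedule". Table 2 is therefore the document that fixes what is collected and when.

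**Timing in the text.** The Abstract states: "Assessments occur at baseline, mid-treatment (week 6), end-of-treatment (week 12), and 3- and 6-month follow-ups, with weekly attempt surveillance". The section on ascertainment and adjudication adds that the C-SSRS is used at every scheduled assessment.

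**Timing in the table.** Table 2 has 20 rows and 16 columns, T0 to T15. It has no DSHI-s row. The rows for MADRS, C-SSRS, NIH BFI and FSS are empty at T0 and marked from T1 to T15.

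**The concern.** Two things do not match.

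First, an outcome that is ranked, modelled and named in the objectives has no place in the schedule. Case report forms are normally built from the schedule. If that happens here, the DSHI-s is never given and the second-ranked outcome has no data from its own instrument. An analysis plan governs what is done with data. It cannot supply a measurement that was not taken.

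Second, four scales lack a baseline mark although the text says that assessments occur at baseline. One of them, the C-SSRS, supplies part of the first-ranked secondary outcome. A baseline value not taken before treatment starts cannot be obtained afterwards.

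**Working it through.** No sample size, event count or power figure is involved, so there is no stated figure to reproduce. The check sets Table 2 against the text row by row, then asks whether the planned model survives the missing T0 values.

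**Step 1: marks per row in Table 2 (16 columns, T0–T15).**

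| Scale | Role in the text | T0 | Marks |
|---|---|---|---|
| BSI | first-ranked (ideation) | yes | 16 of 16 |
| C-SSRS | first-ranked (ideation subscale) | no | 15 of 16 |
| DSHI-s | second-ranked (NSSI) | no row | 0 of 16 |
| BDI-II | third-ranked (depression) | yes | 16 of 16 |
| GAD-7 | fourth-ranked (anxiety) | yes | 16 of 16 |
| MADRS | unranked, clinician-rated depression | no | 15 of 16 |
| NIH BFI, FSS | unranked, fatigue | no | 15 of 16 each |

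**Step 2: could this be a fault in reading the table?** That is unlikely for the DSHI-s, because it also has no descriptive subsection under Instruments. It is unlikely for T0 too. The four affected rows are adjacent and each carries 15 marks, while the SCS-R and SAFER rows directly below are marked at T0.

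**Step 3: is T0 the baseline?** The table does not define its columns. However, the sociodemographic and treatment-history rows are marked only at T0, and the weekly follow-up row starts at T1. Reading T0 as baseline is a strong inference, though it is not stated.

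**Step 4: can the planned mixed model be fitted without T0?** Take the fixed effects as group, categorical time and group×time on the 15 visits T1–T15, with 150 participants. The design has 1 (intercept) + 1 (group) + 14 (time) + 14 (interaction) = 30 columns. Its computed rank is 30, so every fixed effect is estimable. For C-SSRS ideation, MADRS, NIH BFI and FSS the model as written can be run.

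**Step 5: what is lost without T0?** For these four scales there is no pre-treatment value to measure change against, none to adjust for, and none to show that the arms started alike. For the DSHI-s, with no visit scheduled, there is nothing to model.

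**The case against.** Several points can be made for the protocol, and most of them stand in part.

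- **The C-SSRS and MADRS outcomes remain analysable.** This stands. A reader might infer from the blank T0 cells that they cannot be analysed as planned. Step 4 shows otherwise, and the plan names no change score or baseline covariate for secondary outcomes. BSI and BDI-II, which cover ideation and ranked depression, both have T0. BSI can also supply the baseline-ideation covariate for the sensitivity analysis of the primary outcome. MADRS is outside the ranking.
- **Some self-harm data are still collected.** This stands too. SAFER is marked from T0 to T15, so it would be wrong to say that the trial collects nothing on self-harm. But the protocol describes SAFER as still in development and not validated, and it is not the ranked measure.
- **A bias or a loss of precision might be inferred.** One could argue that using T1 as baseline would pull the group×time contrast towards zero, or convert the lost baseline into an equivalent sample size. The documents support neither. Nothing designates T1 as baseline, T1 is not expressly placed after allocation, and no correlation between baseline and follow-up is given.
- **The primary outcome might seem compromised by the absent T0 C-SSRS.** It is not. Each reported attempt is dated individually, checked against records where available and adjudicated blind. Only attempts after randomization count.
- **Secondary outcomes are exploratory by declaration.** This is true and lowers the severity. It does not remove the contradiction between the table and the text.

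Hypothesis 3 also mentions satisfaction ratings without naming a form. That detail can be left to later documents and is not part of this point.

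**Conclusion.** The point holds as an internal contradiction that should be corrected before enrolment. Followed as written, Table 2 yields DSHI-s data at 0 of 16 time points for the second-ranked secondary outcome. It also yields no T0 value on four scales, of which the C-SSRS matters most because its ideation subscale belongs to the first-ranked outcome.

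The consequence differs between the two parts. For the DSHI-s, the planned analysis has no data from its named instrument. For the four scales, the planned model can still be fitted, and the loss is the pre-treatment reference, baseline adjustment and balance check. No numerical loss of power or bias can be attached from the documents. The primary Cox analysis is untouched, so this is a should-fix matter and not a threat to the trial's main conclusion.

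The verdict assumes that T0 is the baseline visit and that Table 2 governs data collection, as the Instruments section indicates.

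**What to change.** 1. Add a DSHI-s row to Table 2, marked at T0 and at the main assessments: week 6, week 12, and the 3- and 6-month follow-ups. That is five marks.
2. Add T0 marks for C-SSRS, MADRS, NIH BFI and FSS, to be completed before randomization. That is four marks.
3. Reconcile Table 2 with the Abstract's assessment times, the Instruments section, the section on ascertaining attempts, and the Secondary analyses and Multiplicity paragraphs. State which of T0–T15 are the baseline, week 6, week 12 and follow-up visits, so that the new marks fall in the right columns.

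**Cost.** An amendment to the schedule and the matching REDCap forms, and a few more minutes at baseline and at the main visits. The protocol gives no completion time per instrument, so the longer visits should be checked against its own limit of 60 minutes. Participants already enrolled under the present table could not be given these baseline values retrospectively, so the change should come first.

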
Supplementary Material

Table 1: The structure and components of BCBT (Bryan & Rudd, 2018)

Phase	1	2	3
Sessions	1-5	6-10	11-12
Therapeutic component	Emotional Regulation and Crisis Management	Targeting Belief Systems Related to Suicide	Relapse Prevention
Techniques	Crisis Response Plan; Means restriction counseling; Sleep stimulus control; Relaxation skills training; Mindfulness skills training; Reasons for living list; Survival kitk.	ABC Worksheet ; Challenging Questions Worksheet; Problematic Patterns of Thinking Worksheet; Activity planning; Coping cards.	Relapse prevention task.

Table 2: Assessment schedule

Schedule of Assessments (CONSORT format)

Measure	T0	T1	T2	T3	T4	T5	T6	T7	T8	T9	T10	T11	T12	T13	T14	T15
Sociodemographic	X															
Treatment History	X															
Weekly Follow-up		X	X	X	X	X	X	X	X	X	X	X	X	X	X	X
BSI	X	X	X	X	X	X	X	X	X	X	X	X	X	X	X	X
BDI-II	X	X	X	X	X	X	X	X	X	X	X	X	X	X	X	X
DUREL	X	X	X	X	X	X	X	X	X	X	X	X	X	X	X	X
GAD-7	X	X	X	X	X	X	X	X	X	X	X	X	X	X	X	X
PHQ-9	X	X	X	X	X	X	X	X	X	X	X	X	X	X	X	X
PIL	X	X	X	X	X	X	X	X	X	X	X	X	X	X	X	X
SHS	X	X	X	X	X	X	X	X	X	X	X	X	X	X	X	X
SF-12	X	X	X	X	X	X	X	X	X	X	X	X	X	X	X	X
HCL-32	X	X	X	X	X	X	X	X	X	X	X	X	X	X	X	X
PROMIS Sleep	X	X	X	X	X	X	X	X	X	X	X	X	X	X	X	X
MADRS		X	X	X	X	X	X	X	X	X	X	X	X	X	X	X
C-SSRS		X	X	X	X	X	X	X	X	X	X	X	X	X	X	X
NIH BFI		X	X	X	X	X	X	X	X	X	X	X	X	X	X	X
FSS		X	X	X	X	X	X	X	X	X	X	X	X	X	X	X
SCS-R	X	X	X	X	X	X	X	X	X	X	X	X	X	X	X	X
SAFER	X	X	X	X	X	X	X	X	X	X	X	X	X	X	X	X
SAFER Follow-Up														X	X	X
